Sharing of Results with Research Participants:

As an implementation study that aims to improve clinical care of patients, any relevant clinical data will be shared with patient participants and/or their clinical care team as they would typically be shared through the course of clinical care. This primarily consists of home blood pressure data (intervention arm) and lipid panels, which will result in the electronic health record for both intervention and control participants. Because of the need to maintain the integrity of

the control condition, the prevention nurse will not directly communicate blood pressure or cholesterol results to the control group participants or their providers unless they exceed the safety thresholds defined above. Results of surveys acquired for research purposes only will not be shared directly with participants. At the end of the trial, final aggregate primary results will be disseminated to participants through presentations to local community advisory boards and/or clinic staff at the local sites.

Data Safety Monitoring:

All elements of the data and safety monitoring plan will be reviewed by the IRB at UH and provided to the NIH institute overseeing the project. The study PIs—[name], [name], and [name] together with the UH IRB PI [name]—will share responsibility for monitoring risks to human subjects and implementation of the monitoring plan. The project will utilize existing medical referral sources and physicians knowledgeable about HIV to address any physical risks that might arise. Serious adverse events will be reported promptly to the institution’s IRB and project officer of the funding source. Monitoring procedures and reporting and action plans for data and safety-related risks are described below. The Data and Safety Monitoring Plan includes the following components which will be addressed individually below:

- Regulatory Issues
- Data Safety and Monitoring Board
- Data Validity/Integrity
- Protocol Compliance
- Termination for Significant Risk

Each of these components have multiple procedures to safeguard the wellbeing of study subjects and to maintain the scientific integrity of the project while achieving the study’s specific aims. Key components of the data and safety monitoring plan include weekly meetings of core members of the research team (at minimum, the Principal Investigators, Project Director and Research Assistants) and monthly meetings of the extended research team including [name], [name], [name], [name], [name], [name], [name], [name], site prevention nurses and research coordinators.

Meetings of Core Members of the Research Team:

The PIs will run monthly conference calls with the entire study team which will include core protocol team along with study coordinators, prevention nurses, and other representatives from each of the 3 study sites. The agenda for these meetings will include tracking of subject recruitment, enrollment, and retention; data collection and entry; and documentation and review of any subject concerns or adverse effects. These meetings will help ensure that the project timeline is being met.

Regulatory Issues

Adverse Events Protocols:

An adverse event is defined as any reaction, side effect, diagnosis or untoward event that either a) occurs during the course of the clinical trial and was not present at baseline; or b) was

present at baseline and appears to worsen during the study. All AE's will be reported to one of the study PIs. All subjects will be aware of their rights prior to participation and will be encouraged to report any incidents or adverse effects to the investigators and the Case Western Reserve University Institutional Review Board (IRB). Contact information for the investigators and the IRB will be provided in all the consent materials. During assessments the research staff will inquire about AEs and complete an AE form for each subject. In the event that the participant is experiencing a worsening of symptoms, the Research Assistant will, with participant's permission, inform the clinic director. The study PIs, and research staff will together determine if the AE places the participant at risk if study treatment is continued.

All adverse events, with the exception of clinically insignificant events and minor common illnesses and injuries (e.g., cold/flu, scrapes, upset stomach, low-grade headaches) will be documented on an AE Log. Should any study subjects express concerns about the study and/or their participation in the study or express distress as a result of their participation, the witnessing research team member will document this in the AE Log. AEs will be reported to the study PIs and the study research staff to determine whether and what actions might be appropriate. Any AEs determined to be serious and/or study-related will require the completion of an AE form to be entered into the project database.

During research staff training, procedures for AE identification, collection and reporting will be reviewed in detail. Study staff will be trained to provide crisis intervention and referral as is standard operating procedure within each clinic for such situations, should they become dangerous or life-threatening (i.e. suicidal ideation or attempts).

AEs will be managed in conjunction with clinic medical staff, with permission from the participant. All subjects will be ongoing patients at a study site clinic and thus subjects can be monitored and have access to medical staff throughout the study period.

Data and Safety Monitoring Board

According to guidelines established by the NIH for clinical trials, the investigators will establish a Data and Safety Monitoring board (DSMB) composed of independent research scientists not otherwise connected with the study. This committee (which is independent of the study investigators) will be set up to monitor the study results for evidence of adverse or beneficial treatment effects throughout the study period. The Monitoring Committee will remain "blinded" to outcome characteristics of the study for as long as possible. While the committee may have access to information that is deemed necessary to make an appropriate determination, highly sensitive information in relation to the outcome of the study will be requested on a "need to know" basis as it may arise during the course of the committee's deliberations. The committee's concerns will be directed to patient accrual rates, appropriate follow-up, compliance, data acquisition, undue complications, and whether the study as it is currently being conducted will be able to answer the proposed hypotheses. Additional responsibilities will include monitoring the integrity of data collection, reviewing training and compliance with all components of the interventions and monitoring for adverse events. The membership and frequency of meeting are at the discretion of the funding institute but will consist of 3-5 members with appropriate expertise, for example in biostatistics, cardiovascular disease, behavioral interventions, HIV research, and clinical trials. It is expected that this committee will meet once per year in person and once via conference call and will report to the funding institute on scientific and administrative issues. We do not anticipate any real harm to patients, but adverse

events will be monitored. Adverse event forms will be used to report all unanticipated events. The following information will be included in the report: date of event, attribution to intervention, and outcome of adverse events. Death will be reported within 24 hours. Unanticipated adverse events will be reported within 7 days. Reports will be submitted electronically to the CWRU IRB and NIH. A written follow-up will be submitted within 30 calendar days. All adverse events (serious or not, related or unrelated, anticipated or unanticipated) will be reported in the annual report to the CWRU IRB and NIH.

The DSMB members and contact information is shown in the following table (members appointed Jan 2019):

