PLHIV (n=110; n=35 per site)	
 1. Age \geq18 years 2. Confirmed HIV+ diagnosis 3. Undetectable HIV viral load: defined as the most recent HIV viral load $<$200 copies/mL, checked within the past year (assessed via chart abstraction), and 4. Hypertension without hyperlipidemia (both defined in parent trial), or 5. Hypertension and hyperlipidemia but unable/unwilling to enroll in the parent trial. 6. Previously enrolled in the parent trial and interested in improving hypertension management through a virtual format. 	Same as parent trial criteria outlined in aim 2.

Withdrawal:

Throughout all phases of our study, subjects will be encouraged to complete the full course of the study assessments. However, it is understood that a subject may discontinue study

participation at any time for any reason. The reason for early withdrawal must be documented in the subject's case file and in the subject tracking document.

Reasons for Withdrawal: Subjects are free to withdraw from the study at any time for any reason. Subjects should normally be withdrawn from the trial if a serious adverse event (SAE) occurs. Subjects **must** be withdrawn from the trial if:

1. They withdraw their consent;
2. The investigator considers it in the best interest of the subject that he or she is withdrawn;

The reason for any subject's discontinuation and the date of withdrawal will be recorded in the subject's case file. The subject's case file, which will be completed up to the point of withdrawal, will be retained for three years. The study report will include reasons for subjects' withdrawals as well as details relevant to the subjects' withdrawals. Any subject withdrawn from the trial prior to completion will undergo all procedures indicated in this protocol as being scheduled to occur at discharge or upon early withdrawal. Any subject withdrawn due to an adverse event (whether serious or non-serious) or any clinically significant abnormal laboratory test value will be evaluated by the Principal Investigator or a monitor (see Key Personnel), and will be treated and followed up until the symptoms or values return to normal or acceptable levels, as judged by the Principal Investigator. Relevant post-study procedures will be performed, wherever possible, on subjects who elect to withdraw.

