Handling of Withdrawal: If a subject is withdrawn from participation in the study at any time at his or her request, at the IRB or Principal Investigator's discretion, the reason(s) for discontinuation shall be documented thoroughly in the source documents and subject's case file. If a subject is discontinued because of an adverse event, this event will be followed until it is resolved or the subject is clinically stable and will also be documented in the source documents and the subject's case file.

8. Study Procedures

Informed consent:

Subjects for each aim will give informed consent to participate in the project. Research Assistants will read, review, and discuss consent forms with all potential participants prior to asking them to sign. If the candidate appears confused or indicates a lack of understanding, the interviewer will attempt to identify the misunderstanding and to explain the form again. Any candidate who still does not comprehend the form will be excluded from the study. We will ask questions to confirm understanding of the material covered in the consent procedure, both open-ended (e.g., "Could you tell me what's going to happen if you enroll in the study?") and closed (e.g., "Will you get free medications from the staff of this research study?" or "what will happen to your medical care after the study?"). Persons who understand the consent form and agree to participate in the study will be asked to sign an authorization for the release of medical information to us. Interviewers will witness and date the signed forms and complete the corresponding. An informed consent checklist will be used to document the participant's understanding of the informed consent process. Consent procedures will take place in a private room or office. Consent forms will be kept in a locked file cabinet within a locked room.

For sub-aim 1.1, we will consent pilot participants once prior to acceptability testing

interview/group discussion and this consent will cover the entire pilot process (acceptability testing, pilot trial procedures, and feasibility testing). For this sub-aim 1.1, we will also be soliciting feedback on the trial design from local HIV Community Advisory Boards (CAB) at UH and Duke as described above. Because there is no identifiable data being collected, we are asking for a waiver of consent for these CAB meetings.

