2. Nurse-managed medication protocols and adherence support. Participants with BP or non-HDL above goal will receive tailored medication management and adherence support. Algorithm-based care to reduce practice variation and clinical inertia has long been recommended to assure that patients are not “stuck” at sub-therapeutic doses of medications⁸². A meta-analysis of nurse and pharmacist-led cholesterol medication adherence interventions showed substantial improvements in adherence and 15-20mg/dL reductions in total cholesterol⁴². By using algorithms and clear decision rules to guide medication titration, the prevention nurse will make recommendations to providers to improve care by reducing clinical inertia, reducing variation, and allowing non-physician staff members to assist in care. A clear and complete algorithm will also help simplify the medical regimen and emphasize medications that are affordable, effective, and have low side-effect profiles.

[figure not shown]
At each visit (in-person or telephone) where recent home BP values (average weekly BP based on a minimum of three values) exceed 130/90mmHg (in line with 2017 ACC/AHA hypertension guidelines), the prevention nurse will review the medication list with the patient, including any recent medication regimen changes and potential side-effects of each medication⁸³. The nurse will provide counseling in several areas, including ways to enhance medication adherence and prevent or ameliorate side effects. For example, patients may be given a personalized medication schedule that shows when they should take their medications.

The prevention nurse will use the algorithms described below to decide on appropriate recommendations for medication changes and will approach the designated responsible provider (HIV, PCP, or non-HIV specialist) for prescriptions and lab orders. *The responsible provider will ultimately decide on final management decisions and may request to have the participant be taken OFF management protocols as clinically indicated (e.g. recent ASCVD events or advanced CKD), in which case the participant would continue all other components of the EXTRA-CVD intervention.*

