For the tertiary outcome of cascade category, we will calculate an ordinal four-level variable at baseline, 4, 8, and 12 months. We will use a proportional odds model fit via generalized estimating equations to examine differences over time between study arms. The proportional odds assumption will be assessed using score tests, and the model will be relaxed to partial proportional odds if necessary. Robust sandwich standard errors will be used to account for potential overdispersion and correlation among the repeated observations over time. Similarly to the primary analysis, the model will adjust for clinic site and include the same general mean model specification. The primary hypothesis will be tested via SAS PROC GENMOD to assess whether the estimated proportions in each level at 12 months differ between arms. All analyses will be conducted following an intention to treat (ITT) principle.

Missing Data:

We will assess mechanisms for missing data in this study. LMM, implicitly accommodates missingness when the response is Missing At Random (MAR); that is, when missingness is due either to treatment, to prior outcome, or to other baseline covariates included in the LMM. We will address missing data by imputing missing values using multiple imputation procedures as described by Schafer. Once missing values have been imputed, each multiply-imputed data set can be analyzed using the LMM. Final parameter estimates and their standard errors will be calculated using Rubin's formula. We will analyze our data and report final study results with and without employing the multiple imputation strategy (compared to complete case analysis) and carefully examine and describe any discrepancies found.

Power:

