The power calculation for this study was based on our prior nurse-led BP intervention¹², a meta-analysis of cholesterol medication adherence interventions⁴², and baseline blood pressure and cholesterol data from our clinic sites. Power estimates were derived empirically via simulation in SAS 9.4. Simulated data were generated based on estimates from prior studies, such that we assumed a mean SBP at baseline of 145mmHg for both arms, with a reduction in the education control arm of 1mmHg by 12 months. For the intervention arm, we evaluated effect sizes (differences from education control at 12 months) of 5-7mmHg. We estimate that 15% of patients may drop out by the 12-month time point, and incorporated missing values into the simulated data based on a uniform pattern of 5% missing at 4 months, 10% at 8 months, and 15% at 12 months. The drop-out rate is consistent with prior interventional studies at our sites (80-88% retention at 12 months).^{11,12,90} We conservatively estimated variance components assuming a total standard deviation of 17 and a within-individual correlation of 0.4 among repeated SBP measurements. Similarly, for the secondary non-HDL outcome, we assumed a baseline value of 132mg/dL with a standard deviation of 41 and a within-individual correlation of 0.7, and evaluated sample size needed over effect sizes ranging from 10-20mg/dL.

After generating 1,000 simulated datasets under these assumptions, we fit the LMMs described above to each and assessed the effect of interest using two-sided tests with a type I

error rate of 0.05. Based on results, we will have >80% power to detect a 6mmHg lower systolic BP and >90% power to detect a 15mg/dL lower non-HDL cholesterol in the intervention arm vs. education control. Table 5 displays the sample sizes needed to detect a range of plausible *clinically significant* BP and non-HDL effects. A 6 mmHg improvement in systolic BP is associated with a ~20% decrease in ASCVD events⁹¹, and a 15mg/dL improvement in cholesterol is associated with ~10% decrease in clinical ASCVD events³¹.

Table 5: Sample size estimates to detect a range of plausible and clinically significant effect sizes						
	BP Effect Size			Non-HDL Effect Size		
	5mmHg	6mmHg	7mmHg	10mg/dL	15mg/dL	20mg/dL
70% Power	278	190	140	248	110	64
80% Power	350	234	178	310	148	80
90% Power	466	340	232	424	184	104

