 162 GENMOD to assess whether the estimated proportions in each level at 12 months differ between arms.

163

164 All analyses will be conducted following an intention to treat (ITT) principle using all available data.
 165 Clinically significant changes specified *a priori* are a 5-point change for SBP and a 15-point change for
 166 non-HDL cholesterol.

167

168 **Missing data**

169 We will assess mechanisms for missing data in this study. LMM, implicitly accommodates missingness
 170 when the response is Missing At Random (MAR); that is, when missingness is due either to treatment, to
 171 prior outcome, or to other baseline covariates included in the LMM.

172

173 Our primary analysis will include all available study-collected data. Those with missing SBP or non-HDL
 174 cholesterol will remain missing for the corresponding cascade, even if EMR data is available for the first
 175 two categories (because it would be missing for the last categories).

176

177 **Attrition bias**

178 As part of our examination of missing data, we will assess differences in baseline characteristics (e.g.,
 179 clinic site, demographics, clinical values, medical history) by retention at each follow up time point. We

180 will use two sample t-tests (or Wilcoxon rank sum tests) for continuous variables and χ^2 tests for
181 categorical variables.

182

183 ***Subgroup analyses and moderation***

184 Pre-specified sub-group analyses of the primary, secondary, and tertiary outcomes will include clinic site,
185 sex, and baseline ASCVD risk (<20% 10-year risk vs. >20% or prior ASCVD). For each category, we
186 will examine the interactions with intervention arm and time. Generally, the modeling approach will
187 mirror that described above for each outcome. Three separate analyses for each outcome will be
188 conducted to assess the effect of each potential moderator. Models will be fit in SAS PROC MIXED and
189 GENMOD, as described above, and the moderating effect of each of the three factors will be assessed via
190 the hypothesis test of the three-way interactions among subgroup, treatment, and time points (4, 8, and 12
191 months). As these analyses are exploratory and hypothesis generating in nature, we will not adjust the
192 alpha value. Interpretation will focus on trends and consistent results over time.

193 Given that some of the participants are treated by study investigator physicians, we will conduct an

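### The protocol makes leaving the trial the default after any serious adverse event, without separating stopping the intervention from ending outcome follow-up; the likely effect on the estimate is small

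*Combined protocol and SAP*

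**What the plan says.** The text on SAE withdrawal is in protocol section 7 (Withdrawal), which is written for all phases of the study. Under Reasons for Withdrawal it states: "Subjects should normally be withdrawn from the trial if a serious adverse event (SAE) occurs". There is no qualifier on relatedness. A separate list gives two reasons for which withdrawal is mandatory: withdrawn consent, and the investigator's judgement of the participant's best interest.

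After withdrawal:
- The participant "will undergo all procedures indicated in this protocol as being scheduled to occur at discharge or upon early withdrawal".
- Under Handling of Withdrawal, where the reason is an adverse event, "this event will be followed until it is resolved or the subject is clinically stable".
- Relevant post-study procedures are done where possible, for participants who choose to withdraw.

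Two other places bear on continuation:
- Intervention component 2 (nurse-managed medication protocols) lets the responsible provider ask for someone to come off the algorithms; the wording is "taken OFF management protocols as clinically indicated (e.g. recent ASCVD events or advanced CKD), in which case the participant would continue all other components".
- The Adverse Events Protocols text says: "The study PIs, and research staff will together determine if the AE places the participant at risk if study treatment is continued".

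On analysis, the SAP (Primary analyses) says: "All analyses will be conducted following an intention to treat (ITT) principle using all available data". Its Missing data section relies on missing at random and names no imputation. The protocol's Missing Data section adds "imputing missing values using multiple imputation procedures" but fixes no imputation model. For planning, the protocol's Power section says: "We estimate that 15% of patients may drop out by the 12-month time point".

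**The concern.** An intention-to-treat comparison needs outcomes after an SAE as much as before it. A participant withdrawn under this rule stays in the model with the assigned arm and earlier blood pressures, so what is lost is the later outcome. The mixed model fills that gap from arm, site and earlier readings, and SAE status is not among its terms. If blood pressure after an SAE runs differently from what those variables predict, the estimate departs from the intention-to-treat effect.

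This loss is one that the protocol itself creates. These people remain patients of the clinics where the outcome is measured, so many of the values could be obtained. The wording also leaves three sites to decide for themselves how often the default applies.

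**Working it through.** **1. Is a 12-month value secured after an SAE withdrawal?** Outcome blood pressure and lipids are scheduled at 0, 4, 8 and 12 months (Aim 2 Procedures). The early-withdrawal procedures mentioned in section 7 are not listed anywhere in the available text. The follow-up required after an adverse event is of the event until it resolves, not of blood pressure to month 12. The where-possible clause covers people who choose to leave. So no 12-month value is required. Some protocol pages were not available, so this is a finding about the available text only.

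**2. The plan's own figure.** Inputs from the protocol's Power section: n = 300, 1:1, SD 17, within-person correlation 0.4, missing 5/10/15% at 4/8/12 months, two-sided 0.05, effect 6 mmHg. Using the generalised least squares variance of the month-12 arm term (common intercept, random intercept per person):
- SE = 1.94 mmHg.
- Power = Φ(6/1.94 − 1.96) = Φ(1.13) = 87.1%, consistent with the stated figure of more than 80%.

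**3. Assumptions the documents do not supply.**
- SAE rate 5% or 10%, equal by arm, spread evenly over the three intervals.
- SAE withdrawals counted inside the planned 15% loss, not added to it.
- Treatment effect building up as 2/4/6 mmHg.
- Control SAE cases follow the usual control course. Intervention SAE cases afterwards lose all, half or none of the benefit, or run 6 mmHg lower than expected at month 12.

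**4. Formulas.** With s the SAE rate and g the mean month-12 departure of intervention SAE cases from the expected course (positive means higher blood pressure):
- Intention-to-treat effect = 6 − s·g. For s = 5%, g = 6: 6 − 0.05 × 6 = 5.70.
- If every SAE case is withdrawn, the model never sees the departure and gives 6.00. Gap = s·g = 0.30.
- If half are withdrawn, the retained half (2.5%) are among the 85% observed at month 12. The model gives about 6 − 6 × 0.025/0.85 = 5.82; the exact least squares value is 5.83. Gap = 0.13.

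**5. Results (mmHg, at SAE rates of 5% / 10%).**

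| After the SAE | ITT effect | Gap (model minus ITT), all withdrawn | Gap, half withdrawn |
|---|---|---|---|
| All benefit lost | 5.70 / 5.40 | 0.30 / 0.60 | 0.13 / 0.25 |
| Half lost | 5.85 / 5.70 | 0.15 / 0.30 | 0.06 / 0.13 |
| None lost | 6.00 / 6.00 | 0 / 0 | 0 / 0 |
| 6 mmHg lower | 6.30 / 6.60 | −0.30 / −0.60 | −0.13 / −0.25 |

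The non-zero gaps are 3% to 31% of the SE (0.06/1.94 to 0.60/1.94). They scale with g: a 10 mmHg departure in one arm with 10% withdrawn would give 1.0 mmHg. Equal departures at equal rates in both arms cancel.

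**6. Precision.** SE and power are unchanged in every row, because total missingness is held at 15%. If SAE withdrawals of 10% or 15% came on top of the planned loss, power would be 83.7% or 81.7%. With every SAE case kept in follow-up, missingness falls to 10% or 5%, SE to 1.89 or 1.84, and power is 88.8% or 90.3%. The model is then within about 0.03 mmHg of the intention-to-treat effect.

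**7. Would the protocol's imputation close the gap?** In a large simulation (10% SAE, half withdrawn, all benefit lost), the intention-to-treat effect is about 5.4. Imputation without SAE status, or with SAE as a main effect only, gives 5.64; imputation with SAE status by arm gives about 5.4. If every SAE case is withdrawn, the SAE-by-arm term cannot be estimated.

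**The case against.** **No contradiction is shown.** A reader might infer that the rule flatly contradicts the two other sections. The documents do not support that. The provider's option under component 2 may concern conditions present at enrolment, since people with prior ASCVD are eligible. The adverse-event text concerns adverse events in general and whether study treatment continues. The SAE sentence is hedged, in contrast to the mandatory list that follows it. This objection stands: the default is unreconciled with the other text but does not contradict it.

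**Mitigating text exists.** Section 7 opens by encouraging completion of all assessments. The SAP compares baseline characteristics by retention. The protocol reports results with and without imputation. The DSMB looks at follow-up. All true, but none of it requires a month-12 measurement for someone whom the protocol has withdrawn.

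**The missing rule may be on unavailable pages.** The data safety monitoring section announces parts on protocol compliance and on termination for significant risk that do not appear in the available text. This stands as a limit on the finding.

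**The size is assumed.** Neither the SAE rate nor the post-SAE blood pressure is documented. A reader might infer that the rule inflates the intervention effect or endangers power. Neither follows: zero and reversed gaps are equally open, and power holds. Loss of all benefit is an upper case, because the drugs are prescribed by the participant's own provider.

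**An unconditional follow-up rule would go too far.** It would override best-interest withdrawal and the IRB's or investigator's discretion, and ignore deaths. This stands, and the replacement wording below allows for it.

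**Conclusion.** The point holds as a minor one. Withdrawal from the trial is the stated default after any SAE, stopping the intervention is not separated from ending follow-up, and the available text secures no 12-month outcome afterwards. Where sites follow the default, obtainable outcomes are lost, and the analysis relies on missing at random with SAE status left out.

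Under the assumed 5% to 10% SAE rate and departures of up to 6 mmHg in the intervention arm, the gap is about 0 to 0.6 mmHg, of unknown sign, and at most 31% of one SE. How often sites would apply the default is not known, so the smaller figures are as plausible as the larger. This would not be expected to change the trial's conclusion; the case for acting is that the remedy costs almost nothing.

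**What to change.** Replace the SAE sentence in section 7 with:

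> An SAE does not by itself end trial follow-up. Intervention components may be stopped case by case. Unless the participant dies, withdraws consent, or the investigator or IRB judges that further assessment is not in the participant's interest, the remaining scheduled blinded 4-, 8- and 12-month BP and lipid assessments are still sought.

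This fits the tailored continuation allowed elsewhere and keeps the existing withdrawal safeguards.

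**Cost.** At 5% to 10% of 300, 15 to 30 participants are affected. With SAEs spread evenly, 3, 2 or 1 visits remain (two on average), so at most 30 to 60 visits are kept out of 300 × 4 = 1,200 planned. No new visit or procedure is added.

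**Optional.** If month-12 systolic pressure is still missing after SAEs, or follow-up has already ended, add one delta-adjusted sensitivity analysis. Impute by arm, then shift the imputed values of intervention SAE cases by −6, 0, +3 and +6 mmHg. SAEs are already recorded in the study database, so no new data are needed. At the assumed rates a 6 mmHg shift moves the estimate by no more than 0.3 to 0.6 mmHg, so its value is mainly reassurance.
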